C. Reintegration	Reintegration success will be evaluated objectively using two different instruments. The first is our recently developed standardized fistula reintegration success measure, the Post-Fistula Repair Reintegration Tool (POFIRT). ¹² The tool has high internal consistency reliability ($\alpha=0.87$) and face validity. ⁷¹ It is a 19-item instrument developed through qualitative work among key informants in Uganda combined with literature review, and incorporates measurement of physical mobility, satisfaction with self-care, participation in work and meeting personal and family needs, participation in social and religious activities, satisfaction with roles in family and community, and comfort with personal relationships. Because only preliminary evidence is available on the POFIRT tool, we will also use the WHO QOL BREF tool to measure quality of life, ⁷² which has been already translated and validated in Luganda by Martin et al. ⁷³
D. Mental Health	Individual mental health measures will target depression, anxiety and traumatic stress, given the substantial rates of these morbidities reported by women with fistula. ^{8,74-76} We will measure depression and anxiety using the Hopkins Symptom Checklist, which has been used in Uganda ⁷⁷⁻⁸⁰ and translated and validated in Luganda. ⁸¹ History of traumatic experiences will be measured by the Brief Trauma Questionnaire (BTQ). ⁸²⁻⁸⁶ Symptoms of trauma will be measured by the PCL-5, a 20-item self-report measure that assesses the 20 DSM-5 symptoms of PTSD and is used to monitor symptom change during and after treatment. ⁸⁷⁻⁹¹ In addition, women will subjectively rate mental health.

E. Physical Health and Health Behaviors	
Physical health will be assessed using the Stanford Self-Rated Health measure for general health⁹², the International Consultation on Incontinence Questionnaire (ICIQ),⁹³ the WHO Disability Adjustment Scale 2.0,⁹⁴ and a list of individual fistula-specific symptoms.
 
Health knowledge and behaviors: Understanding, retention, intent, and behaviors related to health education messaging content will be captured via survey.
 
Adherence: Home implementation of physiotherapy program will be assessed through self report at all non-baseline surveys.

---	--

SAMPLE SIZE

Our sample size of 30 participants with fistula and up to 1 key stakeholders for the pilot study has been calculated based on feasibility.⁹⁵

DATA ANALYSIS PLANS

Quantitative data. Data from surveys will be entered into a password-protected database. Confidentiality will be protected by secure data handling. Data quality practices will include range and logical checks built into data entry, double entry, and error checks. We will examine overall status at each time point for each variable, investigate patterns and types of missing data and non-response, and inspect distributions of mediating and outcome variables to identify outlying or unusual values and assess distributional characteristics. Data analysis: We will describe respondent characteristics and primary outcomes (Aims 1&2 - acceptability and feasibility; section a in Table 2) using frequency tables and descriptive statistics (e.g. means, standard deviations, medians, inter-quartile ranges, and proportions). Preliminary effectiveness (Aim 3) will be conducted by bivariate comparisons of pre vs. post assessments (within our main sample) of reintegration score (primary), quality of life and depression (secondary) and comparison between our external control group using similar data from the same time since surgery using the appropriate distributional tests (paired sample t-test and Stuart-Maxwell tests for pre-post comparison, and two sample t-test and chi-square test for external comparison).

Qualitative data will be recorded and transcribed, and translated into English (if necessary). Thematic analysis will involve a two-stage process⁹⁶. First, data will be coded and classified with transcript review for potential conceptual categories, using the guideline questions as initial categories. Two types of codes will be employed. Deductive codes that represent expected influences on the outcomes will be applied to the data: these will be taken from our qualitative guide informed by Proctor's framework.⁶⁴ Inductive codes emerging organically from the data will be applied: these codes will represent themes unexpected by the researchers and will be identified by recurrence rate and on similarities and differences across the texts. A codebook will include a detailed description of each code, inclusion and exclusion criteria, and examples of the code in use. Coded data will be analyzed to describe the different dimensions and commonalities of each theme, their distribution across participant type and the patterns and linkages between themes. This will allow us to build concepts grounded in the data to explain phenomena. Comparisons will be made with the data to detect divergent views among the participants and to contrast observations that relate to variables within the sample population.

TIMELINE

The planned study timeline is detailed below. We hope to begin participant recruitment in Dec 2020 and anticipate reaching our target sample size within four months. Baseline data collection will occur at recruitment, thus will span this full time period. Data collection for 6w, 3m, and 6m time points are detailed below. Quantitative analysis will occur throughout data collection, with analysis finalized in September 2021. Qualitative data collection will occur from Feb – Jul 2021, with concurrent analysis. Integration of quantitative and qualitative analyses will be done in Sept – Oct 2021. We plan to develop our research proposal for a larger trial to test effectiveness of the intervention from Aug – Oct 2021, submitting to the U.S. National Institutes of Health in October 2021.

Table 3. Study timeline, October 2020 – October 2021

	2020					2021							
	Oct	Nov	Dec	Jan	Feb	Mar	Apr	May	Jun	Jul	Aug	Sep	Oct
IRB review	X	X	X	X	X								
Staff training on intervention protocol			X	X	X								
Participant recruitment					X	X	X						
Quantitative data collection													
Data collection, baseline					X	X	X						
Data collection, 6w						X	X	X					
Data collection, 3m							X	X	X				
Data collection, 6m										X	X	X	
Data analysis						X		X			X	X	X
Qualitative data collection													
In-depth interviews, staff						X	X						
In-depth interviews, providers							X	X					
In-depth interviews, participants								X				X	
Data analysis						X	X	X	X	X	X	X	
Manuscript preparation											X	X	X
Proposal development											X	X	X

SAFETY MONITORING PLAN

POTENTIAL RISKS TO HUMAN SUBJECTS

Potential risks to participants as a result of the pilot study are anticipated to be minimal. Participation is voluntary and participants may decide to discontinue the study at any time. As patients may be sharing potentially distressing experiences and emotional status, they will be provided with counseling within the program, and information on accessing mental health services beyond the program will be shared. Risks to privacy due to personal nature of some questions will be minimized by asking closed ended questions over the phone and conducting in-depth interviews in a private location.

Potentially identifying data that will be collected from participants include names, dates, postal addresses, phone numbers, email addresses, and medical record numbers.

The proposed pilot intervention carries a minimal level of risk; however, we will prioritize participant and data safety, and will implement the following plans for monitoring of our pilot study. No Data and Safety Monitoring Board will be implemented for the current project due to the nature of the intervention and the focus on feasibility and acceptability; however, the PIs and Co-Investigators will closely monitor data and safety related risks to human subjects. Serious adverse events will be reported promptly to the Makerere School of Medicine Research Ethics Committee, the UCSF IRB and the NIH project officer. Risks, monitoring procedures, reporting, and action plans are described below for data and safety-related risks.

DATA AND SAFETY MONITORING

Data-related risks. Potential data-related risks to participants include circumstances where insufficient data was collected for answering the research questions or high/systematic attrition in the trial or intervention participation affecting receipt of adequate intervention dose.

Data monitoring procedures. Overall recruitment goals will be monitored monthly, as well as missing data and follow-up failures. Ongoing monitoring of study progress will be coordinated by [name] [name], Co-PI. No personal identifiers will be included within our databases or in audio recordings of our interviews/focus groups, but linkable identifiers exist separately and the data may be sensitive in nature (e.g., *mental health, incontinence status, gender-based violence*) such that disclosure could provide some risk to the individual. The codes will be stored on a computer that is password protected with a secure server. Transfer or storage on portable devices (e.g., laptops, flash drives) is encrypted. The devices on which this information is stored are accessible only to individuals who need access to these data. Data will not be destroyed until all analyses are complete. Identifiable data will be stored for the amount of time required by the ethical review board. After that point, paper copies will be shredded and electronic copies will be deleted, per UCSF and Makerere policy. A de-identified dataset with associated documentation will be made available to research users, hosted within the UCSF Open Data Repository (DASH).

Data-related risk reporting and action plan. Research assistants will be responsible for compiling numbers of participants recruited, completing required assessments, maintaining databases, and identifying missing data and missing follow-up assessments. Research assistants will prepare recruitment and missing data reports for weekly review by the PIs and Co-Is. All data will be de-identified and stored on a firewall-protected server. Upon recognition of unacceptable recruitment or follow-up rates, or of missing data, the Co-PIs will intervene with strategies to remedy the shortcomings. Intervention completion rates will be monitored.

Safety-related risks. Safety-related risks may include: 1) sensitivity related to questioning about physical and psychological health, 2) release of confidential information about the participant, and 3) recognition of the need for treatment for physical or psychological health concerns.

Safety monitoring procedures. All safety-related risks will be routinely monitored at assessment or intervention session. The security of confidential information will be monitored regularly. Research assistants and intervention moderators will be trained in asking questions about sensitive topics in a caring and non-threatening manner and will stop questioning at the first sign of discomfort or on request. Privacy and confidentiality will be emphasized in intervention sessions with facilitators requesting that participants agree to respect the privacy and confidentiality of other group member, and not to disclose information shared with the group in confidence to anyone outside of the group. Participants will be informed that confidentiality will be maintained for survey and in-depth interview responses. Research assistants will be trained to identify a participant who reports any physical or psychological health concerns, and protocols will be developed to refer participants for treatment.

Safety-related risk reporting and action plan. Research assistants and intervention moderators will report any breaches of confidentiality risks to the Project Coordinator who will then inform the PIs. Any participant in need of treatment due to physical or psychological health concern will be referred for appropriate services per protocol, and the Project Coordinator and PIs will be informed. The PI will be responsible for informing the IRBs through IRB adverse reporting procedure, and the Project Officer through immediate email for life-threatening incidents and through annual report of other incidents per IRB policy. The PI will take appropriate action to stop the study, release a participant from the study, or modify procedures to reduce and/or eliminate the abovementioned risks if they occur at an unacceptable level.

Adverse events. Adverse events will be tracked and referral and follow-up will occur. An adverse event form will be developed to record each incident, actions taken, supervisor notes, and follow-up steps. The form, supplemented by any notes, will be sent immediately to appropriate agencies, including the IRBs, and NIH, with any action recommended by IRB conveyed to the NIH.

Reporting. All problems related to participant safety will be reported to the Makerere University College of Health Sciences School of Medicine Research and Ethics Committee and the UCSF Committee on Human Research and the Committee by the PI within 7 working days. Specifically, we will report in writing: 1) all serious adverse events associated with study procedures, and 2) any incidents or problems involving the conduct of the study or patient participation, including problems with recruitment or consent processes. The PI will provide a discussion of any side effects or problems noticed in the course of the study to the Committee on Human Research on an annual basis.

TRAINING, QUALITY ASSURANCE (QA) AND SUPERVISION

The investigators are experienced in staffing, training, and supervising clinical research studies, including behavioral intervention trials. Our current QA proposal is based on this experience.

Data collector training. Research assistants will be selected based on their prior experience with data collection and familiarity with the study population. We will develop a training manual for the training and ongoing supervision of research staff. An initial training to be led by the PIs and Co-Is will cover: 1)

general research interviewing skills; 2) specific training relevant to this study; 3) extensive training in research ethics and human subjects' protection certification; and 4) observed practice and certification as research assistants.

Assessment quality assurance. The PIs and PM will oversee the QA of data collection and provide feedback and supervision as appropriate.

Intervention training. A training workshop occurs for all intervention staff, and an intervention manual will guide the training and ongoing supervision. This training includes detailed overviews of the intervention approach and procedures, the content covered, and general topics related to intervention research and research ethics. Techniques for adhering to a manualized intervention while allowing flexibility to address individual participant needs will be taught, role-played, and supplemented by instructional readings. Ongoing training will provide updates and troubleshooting on the content area and address any individual supervision or procedural issues in intervention implementation.

Quality assurance of intervention procedures. Intervention fidelity is crucial to maintaining internal validity in intervention trials. Given the nature of the intervention and the clinical issues that arise with this population, facilitators are clinically trained and have knowledge in clinical trials and behavioral science. QA procedures of intervention delivery across facilitators and over time during the course of the study include: 1) development of detailed manuals for each of the sessions; 2) intensive training; 3) incorporation of mock sessions that enable us to ensure that moderators meet performance criteria for intervention delivery, leading to certification of staff based on common performance standards; and 4) QA feedback are incorporated into routine supervision.

Supervision. Separate weekly supervision meetings will be held for data collection and intervention staff, covering progress of the study assessment and intervention protocol problems, providing a setting for staff support and development, and an atmosphere conducive to constructive discussions of dealing with problematic participants and situations. The investigators and project coordinator will schedule individual supervision meetings as appropriate.

POTENTIAL BENEFITS TO HUMAN SUBJECTS

Participants may directly benefit from participation in the intervention if the intervention activities improve their physical and psychosocial symptoms, and improve their quality of life. Potential benefits to society are the development of a model implementable within a referral facility level that can be implemented to improve women's fistula-related outcomes.

PAYMENT

Participants will be provided with a phone and airtime throughout the length of the study, and transportation to and from all clinic visits will be provided. The phone will be kept by the participant after the study is completed (or the participant withdraws from participation). Intervention participants in the nested qualitative research will receive refreshments during the in-depth interviews, be paid the equivalent of \$20 in cash for their participation and will have any transportation-related expenses reimbursed.

ETHICS REVIEW

Approval to carry out this study will be sought from the Makerere University College of Health Sciences School of Medicine research and Ethics Committee (SOMREC) and the Uganda National Council for Science and Technology (UNCST). In the US, we will submit for ethical review at the University of California, San

Francisco Committee on Human Research. Any modifications after initial approval will be reported to the ethical review board(s), trial registry, and all investigators, and approval for modifications will be sought.

DISSEMINATION PLAN

The study team plans to communicate trial results to participants where possible through community meetings and to healthcare professionals and researchers via presentation of findings via academic conferences and publication in peer-reviewed, scholarly journals. Lastly, we will maintain the engagement of several key stakeholders in the development and dissemination of this project, including in data interpretation and ongoing analyses throughout the trial. We will use the International Committee of Medical Journal Editors (ICMJE) criteria for authorship.

APPENDICES

We include the following appendices:

1. Detailed intervention plan
 - a. Health education
 - b. Psychological counseling
 - c. Physiotherapy
 - d. Economic empowerment
2. Informed consent form for study participants
3. Informed consent for key stakeholders (moderators, providers)
4. Study instrument
5. Physical assessment instrument
6. In-depth interview guide
7. Physical examination and physiotherapy referral

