Female genital fistula affects an estimated 2-3 million women globally. Commonly caused by prolonged obstructed labor, female genital fistula has broad physical and psychosocial ramifications, and affected women are stigmatized due to incontinence of urine and/or feces. Despite successful surgery, physical disabilities and poor mental health may persist, making reintegration to family and community difficult for women. The purpose of this project is to conduct a pilot study of a reintegration intervention within the context of clinical fistula care with the objective of improving women's physical and psychosocial recovery. The pilot test is a preliminary phase of a broader research agenda, and the primary outcomes of this study are intervention feasibility and acceptability. We will recruit 30 women to participate in the intervention at the time of fistula repair and will follow them for 6-months. All women will receive the intervention; no comparison group will be included at this stage of the research. Perspectives of up to 10 additional key stakeholders will be sought. Such an intervention has important implications for improving women's health following fistula repair, and may inform service provision for women who undergo surgical repair at the referral hospital level. The proposed intervention pilot lays the groundwork for a subsequent robust trial of intervention effectiveness on women's post-surgical reintegration, physical and mental disabilities, and economic status which is the next step in our research program.

STUDY GOALS AND OBJECTIVES

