Aim 3. To explore the preliminary effectiveness of the pilot reintegration intervention. Within the pilot intervention study, we will explore preliminary effectiveness of the intervention on increases in our primary outcome of reintegration score and secondary outcomes of quality of life and depression through 1) comparison of baseline to six-month scores among intervention participants; and 2) comparison of six-month reintegration, quality of life, and depression scores to six-month data from a different study among women who participated in a longitudinal cohort study of recovery and reintegration in the year following fistula repair.

This proposed research is a first step in moving forward robust strategies for optimizing women's health and quality of life following fistula repair, providing important information on feasibility and acceptability of a multi-component intervention to improve women's physical and psychosocial quality of life in conjunction with fistula surgery within a referral hospital context.

The results from the pilot study will be used to understand and improve feasibility and acceptability of the intervention package, and will inform the development of a subsequent project to test the effectiveness of the intervention among a robust sample size. Data from this study will be an important component of that next proposal.

CENTRAL STUDY HYPOTHESIS. Our central study hypothesis is that the provision of reintegration assistance to women repaired for genital fistula incorporating health education, physiotherapy training, psychosocial counselling and economic empowerment will be feasible and acceptable to intervention recipients and stakeholders.

BACKGROUND AND JUSTIFICATION

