Significant efforts have been made over the past decade to improve surgical capacity for female genital fistula in Uganda. A Ugandan national Fistula Technical Working Group was established in 2002 with representatives from the Ministry of Health, international and national NGOs, medical professionals and media. To date, much of their focus has been on increasing availability of fistula surgery; between 2010 and 2013 the number of women who underwent female genital fistula surgery per year in Uganda increased from 1377 to 2019.²⁵ Fistula surgery is available at 6 centers of excellence in Uganda, with 26 trained surgeons at national and regional referral hospitals. Successful fistula repair ranges 50% - 90% at Mulago Hospital, depending upon fistula severity; regional literature suggests an overall success rate of approximately 70%.²⁶ Despite this wonderful progress in increasing surgical access, very few additional services are being offered to women post-surgically, despite a demonstrated need.

[figure not shown]
Due to the significant physical and psychological disabilities that women experience due to the fistula (Figure 1), targeted rehabilitation efforts are necessary to improve recovery and quality of women's lives. In addition to severe tissue damage, obstructed labor resulting in fistula can cause nerve damage, injury to the uterine cervix and pelvic bone trauma which present as gait disorders, secondary infertility or other reproductive challenges such as increased rates of spontaneous abortion and stillbirth in future pregnancies.^{6,27-29} Many women report experiencing substantial general pain and weakness that persists even after surgery^{5,30} gynatresia and dyspareunia, and high rates of psychiatric morbidity including depression, which may not completely resolve after surgical treatment.^{2,5,8-10,31,32} Our formative research in Uganda revealed that by twelve-months post-surgery, one-third of women continued to experience urinary incontinence, 17% reported weakness, and 9% reported general pain.¹¹ Furthermore, experience of persistent physical symptoms to be associated with substantially lower psychosocial health. For example, at twelve months, women with persistent physical symptoms had mean reintegration score of 21.9 points lower (95% CI -30.2, -13.5)¹², mean self-esteem of 21.2 points lower at twelve months (95% CI -30.1, -12.4), and mean quality of life of 22.5 points lower (95% CI -28.9, -16.1) compared to women

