We propose concurrently targeting four specific areas to improve the lives of women that have suffered from fistula including health education, physical rehabilitation, psychosocial therapy, and economic empowerment. Informed by theoretical frameworks adopted from the interdisciplinary fields of health behavior, women's empowerment, and implementation science and the developing evidence base previously discussed, addressing each of these areas will assist women in overcoming the mental and physical disabilities that they may have suffered as a result of the fistula (physical rehabilitation and psychological therapy), ensure they are appropriately educated about fistula and reproductive health for optimizing recovery and enhancing post-repair health (health education) and address their economic needs to improve quality of life and prevent fistula recurrence in subsequent delivery by achieving the status and financial standing to access timely obstetric care (economic empowerment). In addition, certain components of our anticipated intervention will be directly targeted to women's partners or close family members, who are important sources of social support and critical links between afflicted women and their communities. This will be the first rigorously designed and evaluated multi-component intervention to address all these theoretically important supports for female genital fistula reintegration to our knowledge.

Figure 1. Conceptual Framework Informing Intervention Needs of Women with Genital Fistula

APPROACH

OVERVIEW OF STUDY DESIGN

Given the pilot nature of the current project and our primary objective to understand intervention feasibility and acceptability outcomes, we propose a quasi-experimental design for the current study. The study is being done to inform the subsequent development of a cluster-randomized controlled trial to estimate impact on effectiveness; however, no randomization will be undertaken at this stage of the research, and all women enrolled in the study will participate in the intervention. Assessment of preliminary effectiveness (Aim 3) in the current pilot study is exploratory, and will include change over time from pre-surgery as well as comparison with existing data from similar women that was collected within the context of a different research study.

STUDY SETTING

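### Aim 3 counts the baseline-to-six-month change as preliminary effectiveness of the intervention, but that change also contains fistula repair and recovery, and the plan does not say so

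*Combined protocol and SAP*

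**What the plan says.** Specific Aims, Aim 3, sets out to explore preliminary effectiveness of the intervention on reintegration score (primary), quality of life and depression. It names two routes side by side: a "comparison of baseline to six-month scores among intervention participants", and a comparison of six-month scores with six-month data from an earlier longitudinal cohort of women after fistula repair. Study Participants describes that cohort as 60 women at Mulago Hospital in 2015-2016.

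Data Analysis Plans repeats both routes and assigns the tests: "paired sample t-test and Stuart-Maxwell tests for pre-post comparison, and two sample t-test and chi-square test for external comparison". The cohort route is a "comparison between our external control group using similar data from the same time since surgery". Neither route is ranked above the other, and no adjustment is mentioned.

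On design, the Project Summary states: "All women will receive the intervention; no comparison group will be included at this stage of the research". Overview of Study Design confirms that there is no randomization and says of the preliminary-effectiveness assessment that it "will include change over time from pre-surgery as well as comparison with existing data from similar women". The same sentence limits its status: "Assessment of preliminary effectiveness (Aim 3) in the current pilot study is exploratory".

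**The concern.** A within-group change can be credited to an intervention only if nothing else is expected to move the score over the same period. Here every woman also has fistula repair and six months of recovery. The change is the sum of surgery, recovery and intervention, and a single-arm design cannot split it. The null hypothesis of the paired test is no change after repair plus intervention, not no effect of the intervention. The Stuart-Maxwell test has the same limit for categorical outcomes.

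The aims, design overview, measures and analysis sections do not acknowledge this. Study Measures says only that the longitudinal design avoids the biases of retrospective studies, which is a different matter. Aim 3 states that data from this pilot will be an important part of the next proposal, so a gain due mainly to repair could be carried forward as an intervention effect size.

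**Working it through.** The plan has no figure to reproduce: 30 women is a feasibility number, and no alpha, SD or effect size is given. The main argument is structural; the arithmetic only shows scale, for reintegration score.

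**Inputs from the protocol**
- Repair success: "Successful fistula repair ranges 50% - 90% at Mulago Hospital, depending upon fistula severity" (Background and Justification). The same sentence gives about 70% overall from regional literature.
- Reintegration at 12 months is 21.9 points lower in women with persistent physical symptoms, 95% CI 13.5 to 30.2 (Study Goals and Objectives).
- 30 pilot women; 60 cohort women.

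**Assumptions not in the documents**
- Two-sided 0.05, with all 30 women followed.
- SD of the score 15-20 and pre-post correlation r of 0-0.5.
- Women start near the symptomatic level, and a successful repair recovers the 12-month gap D.
- The intervention effect is exactly zero.

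The SD range has one loose anchor. The reported CI implies SE = (30.2 - 13.5)/(2 x 1.96) = 4.26. With 58 women (inferred from the symptom percentages) and 19 to 29 of them symptomatic, SD = 4.26/sqrt(1/n1 + 1/n2) = 15.2 to 16.2, if the contrast was a simple difference.

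**Step 1: gain without any intervention effect.** Gain = success share x D.
- D = 21.9: 0.7 x 21.9 = 15.3 points.
- D = 13.5: 0.7 x 13.5 = 9.45 points.

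**Step 2: SD of change** = SD x sqrt(2(1 - r)).
- Smallest: 15 x sqrt(1) = 15.0.
- Largest: 20 x sqrt(2) = 28.3.

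**Step 3: chance that the paired test is significant** (noncentral t, 29 df, critical value 2.045, noncentrality = gain/(SD of change/sqrt(30))).

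| D | SD of change | Noncentrality | P(significant) |
|---|---|---|---|
| 21.9 | 28.3 | 2.97 | 0.82 |
| 21.9 | 15.0 | 5.60 | >0.99 |
| 13.5 | 28.3 | 1.83 | 0.42 |
| 13.5 | 15.0 | 3.45 | 0.92 |

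If the spread between women who gain and women who do not is added to the variance (21.9² x 0.7 x 0.3 = 100.7), the D = 21.9 range becomes 0.77 to 0.99. The conclusion is the same.

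**Step 4: precision of the cohort route.** 95% CI half-width = 1.96 x SD x sqrt(1/30 + 1/60): 6.6 points at SD 15 and 8.8 at SD 20.

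**Step 5: what baseline means.** Overview of Study Design takes the change from before surgery. Recruitment and Enrollment allows approach several days before it. The intervention timeline and Appendices 1A, 1B and 1C schedule pre-operative sessions. Study Participants, however, makes women eligible after surgery, and Study Procedures takes baseline immediately after enrollment. On a post-surgery baseline, the change would lose the step across the operation but would still mix recovery with intervention.

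**The case against.** The strongest reply is that the plan already has the right safeguards. Aim 3 is exploratory, effectiveness is deferred to a later cluster-randomized trial, and the central hypothesis concerns feasibility and acceptability only. The second route uses women who also had repair, at the same time since surgery. This stands, and it limits the point to labelling and to which contrast carries an effectiveness statement. It does not remove the point: exploratory describes how strong the evidence is, not what the contrast measures, and the two routes are offered as parallel.

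The figures are also open to fair criticism. The 21.9 points are a 12-month association between women, not a six-month gain within women, and no document supports using them that way. The 50%-90% success range depends on severity and is not a range for a mixed sample, which is why the calculation uses about 70%. The percentages show scale only.

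Three stronger readings are tempting, and the documents do not support them:
- A reader might infer that the plan will declare the intervention effective on a significant paired test. It sets no alpha, threshold or claim rule for Aim 3.
- A reader might see a conflict over six-month follow-up mode, because Study Measures mentions phone or in person. That sentence covers the surveys as a whole and fits the six-week visit in person and the three- and six-month interviews by phone.
- A reader might treat the added Kawempe site as a major source of bias in the cohort comparison. Study Setting says the same team operates at both hospitals, so it deserves a mention and no more.

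**Conclusion.** The point holds as a matter of interpretation and should be fixed. The pre-post change does not isolate the intervention, and the protocol does not say so. This needs no numerical assumption. Under the assumptions listed, a significant paired test with no intervention effect would be likely: about 82% to nearly 100% of studies at a 21.9-point gap, and 42%-92% at 13.5.

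The cohort comparison is the better basis for any statement about the intervention, but it is not a clean one: it is historical, unadjusted and imprecise. The consequence is confined to an exploratory aim and to what is carried into the next proposal. Feasibility and acceptability are unaffected. Quality of life and depression were not modelled, although the structural argument applies to them equally.

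**What to change.** 1. In Aim 3 and Data Analysis Plans, label the pre-post result *change after surgery plus intervention*. Report it with a 95% CI, and do not present it as evidence of, or an effect size for, the intervention.
2. Base any preliminary-effectiveness statement on the six-month cohort comparison, with a 95% CI. Adjust for baseline score where the cohort holds a comparable one; otherwise call the comparison unadjusted. State that calendar period and fistula severity may differ, and note the added Kawempe site together with the shared surgical team. Show repair outcome in both groups if available.
3. Reconcile the eligibility wording in Study Participants with Overview of Study Design, Recruitment and Enrollment, the intervention timeline and Appendices 1A to 1C. State one baseline time point relative to surgery, because it determines what the pre-post change contains.

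The cost is wording plus minor extra analysis, with no new participants or visits. Baseline adjustment and the repair-outcome display depend on cohort data that the protocol does not confirm. Adjustment would not remove confounding by period or severity. The downside is a less favourable headline result.
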